### 6.5.3.1.2. Analysis

The distribution of PFS will be compared between the 2 randomized treatment arms using a 2-sided, log-rank test stratified by histology type, squamous versus non-squamous based on IWRS.

Hazard ratio and corresponding 2-sided 95% CI will be estimated in a stratified Cox proportional hazard model using randomized arm as a single covariate. The PFS curves for each treatment arm will be estimated using the Kaplan-Meier product-limit method. Two-sided, 95% CI for the first quartile, median, and third quartile of PFS will be provided. Progression-free survival rates at fixed time points (every 3 months) will be estimated using Kaplan-Meier estimates on the PFS curve for each randomized arm provided minimum follow-up is longer than time point to generate the rate. The PFS rates will be compared using a normal approximation for the difference of the rates between the 2 randomized treatment arms. Associated 2-sided 95% CIs will be calculated.

Restricted mean difference in PFS will be calculated. Following the suggestion of Karrison (1997), the restriction time T will be chosen as largest time point t such that the standard error (SE) of the survival estimate at time t in each treatment group is no more than 0.075. For this purpose, we will use the simple, albeit conservative, formula proposed by Peto et al. (1977) for calculating the SE of S(t) as:

$$SE(S(t)) = S(t)\sqrt{1 - S(t)/n(t)}$$

where n(t) is the number of patients still at risk at time t.

#### **6.5.3.2. Overall Survival**

Overall survival is defined as the time from the date of randomization to the date of death due to any cause. Patients who are alive will be censored at the date last known to be alive.

Overall survival will be analyzed in a similar manner as PFS. Duration of follow-up will be summarized.

#### **6.5.3.3. Disease Control Rate**

Disease control rate is defined as the proportion of patients who achieve SD plus CRs and PRs.

Disease control rate will be analyzed with CMH test stratified by the histology type.

#### **6.5.3.4. Duration of Response**

Duration of response is defined as the time from the date of first documentation of objective tumor response criteria for CR or PR (whichever is first recorded) to the date of the first documentation of tumor progression (clinical progression or progression per scans) or death due to any cause, whichever occurs first. If a patient does not progress following a response, then their duration of response will use the PFS censoring time.

The analysis of response duration will only include ITT patients with CR or PR. Duration of response will be summarized with descriptive statistics (median and 95% CI) for each treatment arm using the Kaplan-Meier method.

Duration of CR is defined as the time from the date of first documentation of objective response criteria for CR to the date of documentation of tumor progression (clinical progression or progression per scans) or death, whichever occurs first.

Duration of SD is defined as the time from randomization until the criteria for progression are met (clinical progression or progression per scans or death, whichever occurs first).

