INTERIM ANALYSIS:	A planned interim analysis may be performed when the 50th randomized patient has been followed up for approximately 3 months. No statistical boundaries or alpha spending will be applied for this interim analysis as the primary purpose of this analysis is to assess safety and PK. At the time of interim data lock, all patients on study will continue on the study per protocol. See Table 6 for the schedule of analyses of key endpoints.
STATISTICAL METHODS: EFFICACY ANALYSES	All efficacy analyses will be based on the Intent-to-Treat (ITT) population, which includes all randomized patients regardless of whether the patient receives any study drugs or has any efficacy assessments. The primary efficacy endpoint is objective tumor response assessed according to RECIST v.1.1 criteria. The ORR will be summarized and compared using a Cochran-Mantel-Haenszel 2-sided test at a type I error rate of 10% stratified by tumor histology (squamous vs non-squamous.) Progression-free survival will be compared in the 2 randomized treatment arms using a 2-sided log-rank test, stratified by the tumor histology. Progression-free survival time will be summarized using the Kaplan-Meier method to estimate the median PFS and 95% confidence interval (CI). Overall survival will be summarized in the same manner as the PFS.
SAFETY ANALYSES	Safety Population includes all randomized patients who received any amount of study drug. Trial treatment exposure will be summarized. Adverse events will be summarized in terms of treatment-emergent events defined to be any event that begin or worsen in grade after first dose through 30 days after the last dose of trial drugs. Descriptive statistics of safety will be presented using NCI-CTCAE version 4.03 by treatment arm. All treatment-emergent AEs, due to any cause, treatment-related AEs, AEs leading to discontinuation from the trial treatments, SAEs, and drug-related SAEs will be tabulated using worst grade per NCI-CTCAE v4.03 criteria by system organ class and preferred term. On-trial lab parameters including hematology and chemistry will be summarized using the worst grade per NCI-CTCAE v4.03 criteria.

Table of Contents

CLINICAL TRIAL PROTOCOL	1
CONFIDENTIAL INFORMATION	1
PROTOCOL APPROVAL PAGE	2
PROTOCOL ACCEPTANCE PAGE	3
SUMMARY OF CHANGES	4
PROTOCOL SYNOPSIS	7
TRIAL GLOSSARY	21
1.0 BACKGROUND AND RATIONALE	24
1.1 Non-Small Cell Lung Cancer	24
1.2 AM0010 Background	25
1.2.1 AM0010 Mechanism of Action	25

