10.6.3.2 Secondary Efficacy Analyses

PFS will be summarized by median PFS (including 95% CI) for each treatment arm along with the hazard ratio (including 95% CI). The Kaplan-Meier curve for PFS will be presented for each treatment arm and the difference in the curves will be tested using the stratified log-rank test.

Overall survival will be summarized by median survival time (including 95% CI) for each treatment arm along with the hazard ratio (including 95% CI). The Kaplan-Meier curve for survival will be presented for each treatment arm and the difference in the curves will be tested using the stratified log-rank test.

Disease control rate will be analyzed in the same manner as objective tumor response.

Duration of response is defined as the time from the date of the first documentation of objective tumor response (CR or PR), as determined by the Investigator using RECIST v.1.1, that is subsequently confirmed to the date of the first documentation of objective tumor progression or to death due to any cause, whichever occurs first. Duration of response will

be censored on the date of the last tumor assessment on trial for patients who do not have objective tumor progression and who do not die due to any cause while on trial. For patients who have an ongoing objective response but discontinued to have tumor scans assessments before disease progression, the duration of response will be censored at the date of the last tumor assessment.

Duration of response will be estimated for each treatment arm using the Kaplan-Meier product-limit method for patients who have CR or PR. Duration of SD will be summarized as well.

Time to response is defined as the time from date of randomization to the date of the first documentation of objective tumor response that is subsequently confirmed. Duration of response and time to response will only be evaluated in patients with objective response of CR or PR and will be summarized by trial treatment arm.

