### 4.2. Secondary Objectives

The secondary objectives of the study are to compare AM0010 plus pembrolizumab versus pembrolizumab alone with respect to each of the following:

- progression-free survival (PFS)
- overall survival (OS)
- disease control rate (DCR)
- duration of response (DOR)
- safety and tolerability profile

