### 5.2. Determination of Sample Size

With 100 patients, this study has more than 80% power to detect a 25% improvement (ie, 45% versus 70%) in the ORR between AM0010 in combination with pembrolizumab and pembrolizumab alone at a 1-sided 5% type I error rate.

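### Duration of response is listed for comparison between arms, but its only analysis is a descriptive Kaplan-Meier median in responders, which is not a randomized comparison

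*SAP*

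**What the plan says.** SAP 4.2 introduces its list, which includes DoR, with "The secondary objectives of the study are to compare AM0010 plus pembrolizumab versus pembrolizumab alone with respect to each of the following". The objectives in the protocol synopsis also speak of comparing the arms. Protocol 2.2 is weaker: there DoR is only to be evaluated.

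SAP 6.5.3.4 sets the analysis set: "The analysis of response duration will only include ITT patients with CR or PR". It then sets the method: "Duration of response will be summarized with descriptive statistics (median and 95% CI) for each treatment arm using the Kaplan-Meier method". Protocol 10.6.3.2 agrees on both points: "Duration of response will be estimated for each treatment arm using the Kaplan-Meier product-limit method for patients who have CR or PR", and "Duration of response and time to response will only be evaluated in patients with objective response of CR or PR".

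Neither document gives a difference, hazard ratio, test, all-randomized version or sensitivity analysis for DoR. SAP 6.5.2.3 and 6.5.5 list sensitivity analyses for ORR, PFS and OS only. By contrast, ORR, DCR, PFS and OS are compared in all randomized patients, and SAP 6.5.3.1.2 adds a restricted mean difference for PFS. The synopsis states the general rule: "All efficacy analyses will be based on the Intent-to-Treat (ITT) population, which includes all randomized patients".

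**The concern.** Response is observed after randomization and is the primary outcome. Restricting DoR to responders therefore gives up the balance that randomization provides. If AM0010 raises the response rate as hoped, Arm 1's responder set contains patients with no counterpart among Arm 2's responders. Side-by-side medians then mix two things: how long responses last in patients who would respond on either treatment, and how long they last in patients who respond only on the combination. A lower Arm 1 median could appear although no patient has lost any time in response. A higher one could appear although no shared responder has gained any.

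At stake is how a listed secondary objective is answered. As planned, two medians will be reported side by side, and no analysis will say whether randomized patients spend more time in response on the combination.

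**Working it through.** **Inputs.** From SAP 5.2: ORR 45% against 70%, 100 patients, one-sided 5% error. From SAP 5.1: 1:1 allocation, so 50 per arm. The DoR medians used below are assumptions; the documents give none.

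**Step 1: the plan's own figure.** SAP 5.2 claims "more than 80% power to detect a 25% improvement (ie, 45% versus 70%) in the ORR". With pooled rate 0.575, the standard error under the null is √(2 × 0.575 × 0.425/50) = 0.0989. Under the alternative it is √(0.45 × 0.55/50 + 0.70 × 0.30/50) = 0.0957. Then z = (0.25 − 1.645 × 0.0989)/0.0957 = 0.91, and power is 81.9%. The statement is reproduced.

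**Step 2: how far the responder sets differ.** Expected responders are 50 × 0.45 = 22.5 in Arm 2 and 50 × 0.70 = 35 in Arm 1. Let q be the proportion of patients who would respond under either treatment. The share of Arm 1 responders who would not have responded on pembrolizumab alone is (0.70 − q)/0.70. Since q cannot exceed 0.45, the share is at least 0.25/0.70 = 36%. It equals 36% only if every pembrolizumab responder also responds on the combination. Since q cannot be below 0.70 + 0.45 − 1 = 0.15, the share is at most 0.55/0.70 = 79%.

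**Step 3: effect on the responder median (illustration).** Take the 36% case. Let DoR be exponential, with median m1 in shared responders (the same in both arms) and m2 in added responders. The Arm 1 median t solves

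0.643 × 0.5^(t/m1) + 0.357 × 0.5^(t/m2) = 0.5, where 0.643 = 0.45/0.70.

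For m1 = 18 and m2 = 6, t = 11.8, because 0.408 + 0.092 = 0.500.

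**Step 4: time in response per randomized patient.** Over 12 months from response onset, with non-responders counted as zero, use R(m) = (m/ln 2) × (1 − 0.5^(12/m)). Arm 2 has 0.45 × R(m1). Arm 1 has 0.45 × R(m1) + 0.25 × R(m2). With R(18) = 9.61 and R(6) = 6.49, Arm 2 has 0.45 × 9.61 = 4.32 months and Arm 1 has 4.32 + 0.25 × 6.49 = 5.95 months.

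| m1 (shared) | m2 (added) | Arm 2 median | Arm 1 median | Arm 2 mean time | Arm 1 mean time |
|---|---|---|---|---|---|
| 18 | 6 | 18 | 11.8 | 4.32 | 5.95 |
| 18 | 9 | 18 | 13.9 | 4.32 | 6.28 |
| 18 | 12 | 18 | 15.5 | 4.32 | 6.49 |
| 18 | 18 | 18 | 18.0 | 4.32 | 6.73 |
| 18 | 24 | 18 | 19.9 | 4.32 | 6.86 |
| 12 | 6 | 12 | 9.2 | 3.90 | 5.52 |
| 12 | 9 | 12 | 10.8 | 3.90 | 5.85 |

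All entries are in months. In every row the shared responders are unaffected by treatment and the extra 25% gain a response. Time in response per randomized patient rises each time, while the responder median falls, stays level or rises according to m2 alone.

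**The case against.** The strongest reply is that the SAP draws no wrong inference. SAP 6.5.3.4 already calls the DoR summary descriptive and plans no test, hazard ratio or difference. The lead-in in SAP 4.2 also covers safety and tolerability, which are only tabulated, so the word *compare* need not promise a formal estimate for each item. ORR and PFS are randomized comparisons in all patients, and DoR shares its end events and censoring with PFS. Responder-only Kaplan-Meier DoR is used consistently in both documents. All of this stands, and it limits the consequence. It does not close the gap: the restricted mean for PFS measures time without progression, not time in response, and duration of CR and of SD also condition on outcome.

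A reader might infer that the planned medians will count against AM0010. The documents do not support that. The fall requires added responses to be shorter, and no DoR figure is given. The one related remark, in Protocol 1.2, describes the duration of responses on the combination as apparently increased, though in small cohorts.

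Simulated chances of a lower observed Arm 1 median (85% with m2 = 6 and 75% with m2 = 9, at m1 = 18) assume complete follow-up. They do not describe the read-outs that SAP 6.8 schedules about 6 and 12 months after the 100th patient is randomized, when many durations may still be censored. Nor is 36% a fixed property of the design; it is a lower bound.

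**Conclusion.** The point holds as a mismatch between a stated objective and its analysis. DoR is listed for comparison in SAP 4.2 and the synopsis, and the plan contains no comparison of it that randomization protects. At the design rates, at least 36% of Arm 1 responders lack a counterpart among Arm 2 responders. This bound follows from the ORR assumptions alone.

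The size and direction of any distortion rest on assumed DoR medians, exponential durations and unchanged durations in shared responders. With shorter added responses, the illustrated Arm 1 median is lower by 2.5 to 6.2 months (shared median 18, added 6 to 12) or by 1.2 to 2.8 months (shared median 12, added 6 to 9). With equal or longer added responses it does not fall. It would go too far to say that the plan is biased against AM0010 or makes an invalid claim, since the medians are descriptive and untested. The primary analysis and sample size are unaffected. This is a cheap improvement, not an error that endangers the trial.

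**What to change.** Keep the responder Kaplan-Meier summary in SAP 6.5.3.4 and add a sentence saying that it is descriptive and is not a between-arm comparison.

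For the DoR objective, add the between-arm difference in restricted mean time in response over all randomized patients, with non-responders contributing zero. In each arm, compute the area between two Kaplan-Meier curves from randomization: PFS, and time to the first of response, progression or death. Use the same censoring rules for both curves and a common, pre-specified restriction time. Report the difference with a 2-sided 95% CI as a supportive, untested analysis. State whether response must be confirmed, because Protocol 10.6.3.2 requires confirmation for DoR and SAP 6.5.3.4 does not.

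This quantity runs from randomization to the restriction time, so its values will differ from the illustration above, which counts from response onset.

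The cost is one added SAP paragraph and one more output to explain beside the conventional median. The dates are already needed for PFS and time to response, and a restricted mean is already planned for PFS. No new data, patients or error allocation are needed.

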#### **6.5.4. Other Efficacy Analyses**

##### **6.5.4.1. Best Objective Response Rate**

Best objective response is calculated based on the overall visit response from each tumor assessment. It is the best response a patient has had following randomization but prior to starting any subsequent cancer therapy, prior to documented progression (clinical progression or progression per scan) or the last tumor assessment in the absence of documented progression and subsequent cancer therapy.

Best objective response will be summarized using the following response categories: CR, PR, SD, progressive disease, and not evaluable.

##### **6.5.4.2. Time to Response**

Summary statistics of time to objective response will be provided for patients who achieve PR or CR. Time to response is defined as the time from the date of randomization and the date of first documentation of objective tumor response, CR or PR (whichever status is recorded first). No censoring observation will occur by definition.

##### **6.5.4.3. Change in Tumor Burden**

Percentage change from baseline in tumor burden will be calculated at each tumor assessment. Best percentage change from baseline in tumor burden will be calculated as the biggest decrease or the smallest increase in tumor burden from baseline.

Tumor burden is defined as the sum of the longest diameters of the target lesions (the measurable tumor lesions).

The percentage change from baseline in tumor burden is calculated as:  $(\text{Sum of target lesions at week } x - \text{sum of target lesions at baseline}) / \text{sum of target lesions at baseline} * 100$

#### **6.5.5. Sensitivity Analyses**

##### **6.5.5.1. Progression Free Survival**

Progression-Free Survival Sensitivity Analysis 1 (PFS event is disease progression per scan or death): clinical progression will not be considered as a progression event.

Progression-Free Survival Sensitivity Analysis 2: (PFS event is the earlier of disease progression per scan, clinical progression, or death): pseudoprogression without confirmation is not considered as an event (progressive disease).

Progression-Free Survival Sensitivity Analysis 3 (PFS event is the earlier of disease progression per scan, clinical progression, death, or initiation of subsequent anti-cancer therapy): patient initiates subsequent anti-cancer therapy will be considered as a progression event at the date of initiation of subsequent anti-cancer therapy – 1 day.

Progression-Free Survival Sensitivity Analysis 4 (PFS event is disease progression per independently reviewed scan or death): clinical progression will not be considered as a progression event.

**6.5.5.2. Overall Survival**

Overall Survival Sensitivity Analysis: Patients who crossover will be censored on the first dose date of crossover – 1 day.

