	
 • Clinical evaluation: complete history, physical examination (Site/Organ System Status [includes: General appearance, skin, H/E/E/N/T – Thyroid, Pulmonary, Cardiovascular, Gastrointestinal, Musculoskeletal/Extremities, Genitourinary/Breast, Lymph Nodes, Neurological, and Psychiatric]), ECOG performance status, height, weight, vital signs, and documentation of concomitant medications. • Laboratory studies: hematology (WBC with differential, RBC count, reticulocyte count, and platelet count); aPTT and International Normalized Ratio (INR) or PT; comprehensive chemistry panel (sodium, potassium, chloride, CO₂, creatinine, calcium, BUN, albumin, AST, ALT, alkaline phosphatase, lactate dehydrogenase, and total bilirubin); Thyroid Function Test (TSH, free T3, and free T4); urinalysis with microscopic examination; and serum or urine pregnancy test for women of child bearing potential. • Pharmacokinetic: sparse sampling in all patients in Arm 1 and crossover and exploratory molecular biomarker sample collection in all patients. • Tumor Assessment: CT or MRI (if allergic to contrast media) scans will be performed every 9 weeks (± 7 days) during the study treatment and during the first year from discontinuation of the study treatment, every 12 weeks (± 7 days) during the second year, and every 16 weeks (± 7 days) thereafter, to evaluate response to treatment by RECIST v.1.1. • Tumor assessment will be repeated until disease progression, death, or receipt of new anti-cancer therapy, or until study completion, whichever is first, whether or not study treatment was administered • The same radiographic procedure to define measurable lesions must be used throughout the trial for each patient. • Patients will continue the assigned trial treatments until tumor progression by RECIST v.1.1 criteria (per Investigator's assessment) by CT or MRI (if allergic to contrast media), withdrawal from the trial, or intolerance of therapy not manageable with dose modifications outlined in the protocol/package insert and/or supportive care. Note: Patients with suspected radiographic pseudoprogression, in the absence of clinical deterioration, should remain on trial treatments and be rescanned at 4 weeks or later. If progression is confirmed on follow-up scan, patients in Arm 1 will be discontinued from the treatment and patients in Arm 2 may crossover to receive treatment with AM0010 with pembrolizumab if they fulfill eligibility requirements. Refer to Section 7.6. • Patients who discontinue trial treatments with response of CR, PR, or SD will undergo CT or MRI scan evaluations per protocol until time of PD or death, or until study completion or initiation of subsequent anti-cancer therapy, whichever is first. • Patients who demonstrate clinical progression will have a scan conducted at the time to document disease status by RECIST v.1.1. • The first scheduled tumor response assessment will be performed at 9 weeks (± 7 days), and responders (CR or PR per RECIST v1.1) will have a confirmatory scan at ≥ 4 weeks after response has been established using the same technique as baseline scans. • To mitigate the chance of detecting false progression (ie, pseudoprogression) early in the course of treatment with AM0010 in combination with pembrolizumab or the pembrolizumab-alone arm, patients whose scans show radiographic progression in the absence of clinical deterioration including worsening performance status as assessed by the Investigator may remain on trial treatments and an additional scan should be obtained at ≥ 4 weeks (± 7 days) as outlined in Section 7.6. If this subsequent scan shows disease progression, patients in Arm 1 will be discontinued from the treatment period of the trial; patients in Arm 2 may cross over to receive treatment with AM0010 in combination with pembrolizumab if they fulfil the necessary eligibility criteria. • All screening and on-trial CT/MRI scans for all patients randomized on the

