3.0 TRIAL DESIGN

This is an open-label, randomized, multicenter, Phase 2 trial in 100 adult male and female patients with treatment-naïve, Stage IV/metastatic NSCLC whose tumors are not known to have EGFR mutations or ALK rearrangements, but have high expression ($\geq 50\%$) PD-L1 as determined with an FDA-approved PD-L1 IHC 22C3 assay.

Patients will be stratified according to tumor histology (squamous vs non-squamous).

Patients will be randomized in a 1:1 ratio into 1 of 2 treatment arms (Figure 1).

[figure not shown]

Figure 1. Trial Design

Trial sites will provide best supportive care per institution's standard of care including concomitant medications.

Arm 1 and 2 treatment will continue in the absence of disease progression, unacceptable toxicity, or patient's withdrawal of consent. Patients will be treated with a maximum of 35 cycles of pembrolizumab every 3 weeks or 2 years, whichever is longer.

All radiological assessments will include at minimum, scans of the head, chest, abdomen, and pelvis.

At the time of documented disease progression (by Investigator assessment) patients in Arm 1 will be discontinued from the treatment period of the trial and continue on the follow-up period. At the time of documented disease progression (by Investigator assessment), patients in Arm 2 may crossover to receive treatment with AM0010 and pembrolizumab.

Confirmation of complete response (CR) or partial response (PR) is required. Confirmatory scans will be performed as follows:

- CR and PR criteria per RECIST v1.1 must be met again at least 4 weeks after initial documentation.

Patients with suspected pseudoprogression on scans in the absence of clinical deterioration should remain on trial treatments and be rescanned at 4 weeks or later as outlined in Section 7.6.

If progression is confirmed on follow up scan, then discontinue treatments and follow trial procedures for end of treatment and survival follow-up or procedures for crossover patients.

Scans will include head and CAPs and will be sent to the central imaging vendor for archiving and possible assessment at a later date. If clinical progression is suspected, all relevant clinical documentation is to be submitted to the central imaging vendor.

For patients who were randomized, but withdraw consent, survival (date of death) will be obtained by use of publicly available information.

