6.3 Dosing Schedule

Patients will be treated on an outpatient basis with AM0010 plus pembrolizumab or pembrolizumab alone (Figure 2).

Arm 1 consists of AM0010 at 0.8 mg for patients \leq 80 kg body weight or 1.6 mg for patients $>$ 80 kg body weight, self-administered SQ QD (abdomen, thigh, or back of upper arm) plus pembrolizumab at 200 mg over approximately 30 minutes IV infusion on Day 1 of a 21-day cycle.

Arm 2 consists of pembrolizumab alone at 200 mg over approximately 30 minutes IV infusion on Day 1 of a 21-day cycle.

[figure not shown]

Figure 2. Dosing Schedule

Patients will continue on treatment until they experience progressive disease per Investigator assessment, unacceptable toxicity, require subsequent anticancer therapy, withdraw consent, or their physician feels it is no longer in their best interest to continue on treatment.

Crossover of patients from the pembrolizumab-only treatment arm (Arm 2) into the pembrolizumab plus AM0010 treatment arm (Arm 1) is permitted at the time of disease progression (as assessed by the Investigator). Supportive care per the institution's normal standard of care, including concomitant medications, can be provided at the Investigator's discretion.

The documentation of the investigational product administration (AM0010) will be noted on the case report form (CRF) page and in the source documentation/patient diary. The date,

dose volume, dose amount, and time of administration for each dose when the PK samples are collected (including the 2-day dosing history prior to a PK draw day), the first and last administered dose for the patient, doses withheld and missed, and dose schedule adjustments will be recorded on the respective CRF page. Details of preparing and administering AM0010 will be provided to the patient and are included in the Pharmacy Binder provided by the Lilly/designee.

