7.8 Continued Treatment

7.8.1 Crossover

At the time of disease progression (as assessed by the Investigator) patients randomized to trial Arm 2 may crossover to study Arm 1 to receive AM0010 and pembrolizumab. When progressive disease is noted on the scan for an Arm 2 patient, no more than 21 days should pass before the patient crosses over to Arm 1. The scans and/or clinical assessment at crossover will be used as a new baseline to determine response or PD on Arm 1.

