### **6.3. Patient Disposition**

A detailed description of patient disposition will be provided. It will include a summary of the number and percentage of patients enrolled in the study, randomized in the study, treated in the study, reasons for discontinuation from study treatment, and reasons for discontinuation from study. If the reason for discontinuation is adverse event (AE), the associated AE term will be reported. Patients who cross over from pembrolizumab to AM0010 in combination with pembrolizumab following progressive disease will be summarized as well.

Protocol violation will be summarized by treatment arm.

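### The only overall-survival analysis that acts on crossover censors Arm 2 patients after progression; this censoring is one-sided and likely informative, so its hazard ratio should not be read as the crossover-free effect

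*SAP*

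**What the plan says.** The main OS analysis uses the ITT population by assigned arm and censors only living patients, at the date last known alive (SAP 6.1.1, 6.5.1.1 and 6.5.3.2). Crossover plays no part in it.

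The single OS sensitivity analysis, SAP 6.5.5.2, reads "Patients who crossover will be censored on the first dose date of crossover" minus one day. It names no test. SAP 6.5.3.2 states "Overall survival will be analyzed in a similar manner as PFS", and the PFS section states "The distribution of PFS will be compared between the 2 randomized treatment arms using a 2-sided, log-rank test stratified by histology type", so a reader would expect the sensitivity analysis to carry a 2-sided stratified log-rank p-value and a Cox hazard ratio.

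Crossover is open to one arm only. Protocol 6.3: "Crossover of patients from the pembrolizumab-only treatment arm (Arm 2) into the pembrolizumab plus AM0010 treatment arm (Arm 1) is permitted" at progression. Protocol 7.8.1: "At the time of disease progression (as assessed by the Investigator) patients randomized to trial Arm 2 may crossover to study Arm 1", within 21 days of progression on the scan. For Arm 1, Protocol 3.0 says that at progression "patients in Arm 1 will be discontinued from the treatment period of the trial and continue on the follow-up period". The Trial Procedures part of the synopsis adds a condition: "patients in Arm 2 may crossover to receive treatment with AM0010 with pembrolizumab if they fulfill eligibility requirements". Protocol 7.8.1 lists no such requirements.

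SAP 6.7.4 deals with crossover for time to progression and adverse events, not for OS. SAP 6.3 plans a summary: "Patients who cross over from pembrolizumab to AM0010 in combination with pembrolizumab following progressive disease will be summarized as well".

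**The concern.** Log-rank and Cox analyses assume that, within an arm, patients censored at a given time have the same later risk of death as those who remain. Here censoring is triggered by progression, a strong predictor of death, and it can happen only in Arm 2. Deaths after progression count in full in Arm 1, while those of Arm 2 crossover patients are removed.

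OS is a secondary objective and crossover is part of the design. A reader will set this hazard ratio beside the ITT one to judge what crossover did. If the two differ, the difference could be a real crossover effect or an artefact of the censoring, and the SAP gives no warning that the second is possible.

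**Working it through.** **The plan's own figures.** The documents give no OS power or event target to reproduce. The only power statement is for ORR (45% vs 70%, 50 per arm, 1-sided 5%). With pooled SE √(2×0.575×0.425/50) = 0.0989 and unpooled SE √((0.45×0.55+0.70×0.30)/50) = 0.0957, z = (0.25 − 1.645×0.0989)/0.0957 = 0.91, so power is about 82%. This agrees with the stated figure, and crossover does not touch it.

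**Inputs from the documents.** Median PFS on pembrolizumab 10.3 months and 6-month survival 80.2% (Protocol 1.1); crossover within 21 days of progression on the scan (Protocol 7.8.1); 3-year OS follow-up after the last randomization (Protocol 3.6).

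**Assumptions, not in the documents.** The share *f* of PFS events that are deaths; post-progression survival; the share of progressors who cross over; how far they are selected on prognosis. For the first two table rows: 18 months' accrual, 12 or 36 months' minimum follow-up, and a two-level prognosis factor, exp(±0.35) or exp(±0.7), on the post-progression hazard.

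**Step 1: which settings fit the protocol's own survival figure?** Take PFS hazard λ = ln 2/10.3 = 0.0673 per month and post-progression hazard μ. Without the prognosis factor,

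S(6) = e^(−6λ) + (1−f)·λ·[e^(−6μ) − e^(−6λ)]/(λ−μ), with e^(−6λ) = 0.668.

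For post-progression medians of 9 and 14 months, μ is 0.0770 and 0.0495, and the ratio [·]/(λ−μ) is 3.89 and 4.23.

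- f = 15%: 0.668 + 0.85×0.0673×3.89 = 0.890, and 0.668 + 0.85×0.0673×4.23 = 0.910. With the prognosis factor the range is about 88–91%, well above 80.2%.
- f = 50%: 0.668 + 0.50×0.0673×3.89 = 0.799, and 0.668 + 0.50×0.0673×4.23 = 0.810. This is close to 80.2%.

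A second way to reach 80.2% is to let *f* run from 20% to 50% and shorten post-progression survival to fit. The post-progression hazard is then 0.240 to 0.0688 per month, a median of ln 2/0.240 = 2.9 to ln 2/0.0688 = 10.1 months.

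**Step 2: why *f* matters.** The bias depends on how much higher the death hazard is after progression than before it. Before progression it is f×λ. At f = 15% that is 0.0101, so the later hazard is 4.9 to 7.6 times as high. At f = 50% it is 0.0336, so only 1.5 to 2.3 times.

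**Step 3: apply the SAP 6.5.5.2 rule with no drug effect.** Large-sample illness-death simulation, crossover delay uniform over 0–21 days, 50% of progressors crossing over. Hazard ratio is Arm 1 vs Arm 2; the ITT value is 1.00 apart from simulation error.

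| Setting | 6-month survival | Crossers like other progressors | Moderate selection of fitter patients | Strong selection |
|---|---|---|---|---|
| f = 15%, post-progression median 9–14 months | 88–91% | about 1.2–1.3 | 1.03–1.22 | 0.86–1.16 |
| f about 50%, median 9–14 months | about 80% | 1.03–1.10 | 0.95–1.07 | 0.88–1.04 |
| f = 20–50%, median 2.9–10.1 months | 80.2% | 1.09–1.43 | 1.01–1.38 | 0.87–1.16 |

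In the first two rows, moderate selection means that 75% of crossers come from the better-prognosis half, and strong means that better-prognosis progressors cross first. In the third row, crossers have 0.7 (moderate) or 0.3 (strong) times the average post-progression hazard.

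**Step 4: with a real effect.** Use the third-row calibration with a hazard ratio of 0.70 on every transition, and on crossers after crossover. At 50% unselected crossover, the no-crossover hazard ratio is 0.65–0.67, ITT gives 0.68–0.72, and the censored analysis gives 0.73–0.93. In each of these settings it lies further from the no-crossover value than ITT does.

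**The case against.** The strongest reply has three parts.

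First, this is a labelled sensitivity analysis of an unpowered secondary endpoint, beside an intact ITT analysis. OS is not a key endpoint of any analysis in the SAP 6.8 schedule, and the p-value is only inferred from other sections. All of this stands, and it is why the consequence is minor. It does not make the hazard ratio interpretable.

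Second, the direction is not settled. A reader might infer that the analysis will routinely be biased against AM0010, by 20% or more. The documents do not support that. The synopsis makes crossover conditional on eligibility, so fitter progressors may be the ones who cross. In the setting with about 50% deaths, moderate selection puts the null hazard ratio on either side of 1. The larger figures need either a 15% death share, which does not fit the quoted 6-month survival, or short post-progression survival, which the documents do not give. For the same reason no particular false-positive rate can be attached to the analysis.

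Third, crossover need not follow at once. With suspected pseudoprogression, a rescan at about 4 weeks or later comes first (synopsis Trial Procedures; Protocol 7.6). That can delay censoring by some weeks, but censoring still follows progression and still falls on Arm 2 alone.

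It is also fair to say that formal crossover adjustment would be fragile with about 50 Arm 2 patients, so it cannot be a requirement.

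**Conclusion.** The concern holds for SAP 6.5.5.2 alone. Independent censoring is implausible there by design, because the trigger is progression and only Arm 2 is exposed to it. The hazard ratio, and any log-rank p-value attached to it, is not a valid estimate of OS without crossover.

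The bias is against AM0010 if crossover patients resemble other progressors; selection of fitter patients shrinks it and can reverse it. With 50% unselected crossover and no drug effect, the two calibrations that fit 80.2% survival at 6 months span 1.03 to 1.43. That range rests on assumed crossover rates, death shares and post-progression survival, none of which the documents state.

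A reader might go further and infer that the trial's OS result is compromised. It is not: the ITT analysis ignores crossover, and the primary ORR test does not involve it.

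**What to change.** In SAP 6.5.5.2:

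1. Keep ITT as the main OS analysis, as planned.
2. Report the crossover-censored analysis descriptively, without a p-value, with this label: *Censoring follows progression in Arm 2 only and is likely informative. It is expected to disfavour AM0010 if crossover patients resemble other progressors, but the direction depends on who crosses over. Not to be read as the crossover-free effect.*
3. Add to the crossover summary in SAP 6.3 the baseline and last available pre-crossover characteristics of the patients who cross over. Last available is the realistic choice: performance status, examination and vital signs are scheduled at odd-numbered cycles (Protocol 7.4.1, Appendix A), and the only assessment that Appendix A names for crossover is a baseline tumor assessment.
4. Optional and supportive only: a crossover-adjusted estimate (two-stage, inverse probability of censoring weights, or a rank-preserving structural failure time model with re-censoring), with its assumptions stated.

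The cost of items 1 to 3 is SAP wording and one small table, with no new visits or data. What is lost is a p-value that is not valid. The trial would also have no single headline figure for OS without crossover.
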